Appendix E

VAS Patient Anxiety

VAS Patient Understanding of Mohs

My Current Level of Understanding
of The Mohs Procedure

Appendix F

[figure not shown]
Mohs Quiz

Thank you for your participation in our study! We ask you to fill out the quiz and choose the best answer for each question. Do not worry about your score, as you cannot fail.

1. What are the main benefits of the Mohs procedure compared to other treatments?

- A) The procedure is faster
- B) The procedure allows for easier repair of the wound
- C) The recovery time is faster
- D) Mohs removes the entire cancer in one procedure and has a higher cure rate.

2. How is the cancer removed in the first stage of the Mohs procedure?

3. How can my doctor be sure that all cancer cells are removed?

- A) You will find out your results in one week after a pathologist views the specimen
- B) A special dye is added that “lights up” in cancer cells
- C) Based on the size of the visible tumor
- D) Your doctor examines the skin under the microscope and maps out any remaining cancer

4. Do all patients require a second stage of cancer removal?

- A) No, a second stage is not necessary if all of the cancer was removed
- B) Yes, a second stage is always removed to help close the surgical wound
- C) No, the Mohs procedure is completed in one layer always
- D) Yes, a few extra millimeters of extra healthy tissue are always removed

5. What are the reasons for a layer-by-layer approach when removing the cancer?

- A) To ensure that the surgical wound can be closed easily
- B) To remove a minimal amount of healthy skin, while removing the whole cancer
- C) There is less bleeding with this approach
- D) To prevent infection

6. Why do Mohs surgeons remove an area of healthy skin around the cancer?

- A) To try to remove all of the cancer in one stage
- B) The visible portion of the cancer is the only portion of the cancer that matters
- C) None of the skin surrounding the cancer is “healthy”
- D) The skin is going to die because it is so close to the cancer

Appendix G

Satisfaction Survey

1. Overall how satisfied are you with today's explanation of the Mohs Procedure?

- A) Not at All Satisfied
- B) Somewhat Satisfied
- C) Neutral
- D) Moderately Satisfied
- E) Entirely Satisfied

2. Do you feel that this explanation can be improved?

- A) Disagree
- B) Somewhat Disagree
- C) Neutral
- D) Somewhat Agree
- E) Strongly Agree

3. Would you recommend that patients be provided an explanation in a similar manner?

- A) Disagree
- B) Somewhat Disagree
- C) Neutral
- D) Somewhat Agree
- E) Strongly Agree

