1.1 Overview

Perioperative anxiety in Mohs Micrographic Surgery (MMS) is associated with increased post-operative pain and decreased patient satisfaction. Optimum delivery of patient education has been suggested as a potential modality to decrease perioperative anxiety, but has not been conclusively demonstrated. A pilot study completed in July 2017 at University Hospital's Westlake Campus demonstrated that patient education completed with a 3D printed model and standardized script increased patients subjective understanding and decreased patient anxiety during the perioperative period. Despite these findings, the pilot study had notable limitations that included a small sample size and lacked an adequate control group. Our aim is to complete a comprehensive randomized control trial, with a larger cohort of patients and an adequate control group, to compare of our innovative counseling protocol to the current standard of care, verbal counseling. This work may help to provide an optimized educational delivery system for MMS at University Hospitals.

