5.0 STUDY DESIGN AND METHODS

A total of 100 patients will be recruited from University Hospitals Department of Dermatology Mohs Micrographic Surgery Clinics at the Cleveland Medical Center, Chagrin Highlands and Westlake Locations. These patients will be randomly assigned to a control (50%) or experimental group (50%) prior to the onset of the study protocol. Patients in the control group will be educated on MMS according to the current standard of care, verbal counselling, with a standardized script (Appendix A). The experimental group will be educated on MMS with a standardized script in addition to a 3D MMS model (Appendix B).

Patients will initially undergo verbal consent in private patient rooms located within the Mohs Microsurgery Clinics prior to study initiation. As previously stated, verbal consent will prevent the

collection of any PHI during this study. Upon verbal consent, patients will fill out baseline testing including a State-Trait Anxiety Inventory (STAI) and Visual Analog Scale (VAS) to quantify their anxiety and understanding of the Mohs procedure (Appendices C, D, E). Following baseline testing, patients will undergo preoperative education. In the control group patients will be educated with a standardized script alone, and experimental group patients with a standardized script, in addition to a 3DP physical model demonstrating the MMS procedure. The total length of time to educate patients will be recorded.

After completion, patients will undergo standard of care procedures with the MMS team, including surgeon, and undergo the first stage of the MMS procedure. Patients will undergo post-testing following the first layer of MMS. This layout was chosen to ensure all patients to prevent study personnel from impeding the workflow of the MMS clinic, and is similar to a workflow used in previous studies.^{4,5}

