- b. Following the objective questions, patients will be provided 3 subjective questions related to their satisfaction with the explanation of MMS that they received. These subjective questions will be used to help delineate subjective differences between the control and experimental groups. Similar objective surveys have been used to assess satisfaction following educational intervention.¹²⁻¹⁸
- c. We propose to hand out this questionnaire following completion of the first stage of MMS.
- d. See Appendix F & G

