5.52 Intervention Administration

The educational intervention will be completed following baseline testing by the research assistant in a private patient room according to the standardized script. If patients have additional questions regarding the study at the time of intervention they will be answered by the research assistant. If these questions pertain to the patients' medical record, protected health information, or specific medical questions related to their MMS procedure the research assistant will defer to the medical team. Patients will receive educational intervention following baseline testing.

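### The Appendix G satisfaction items do not say which explanation to rate, and they are asked after both arms have also had contact with the surgical team

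*Combined protocol and SAP*

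**What the plan says.** - **What is randomised.** Section 5.52: "The educational intervention will be completed following baseline testing by the research assistant in a private patient room according to the standardized script". Both arms hear the script; the experimental arm also sees the 3D printed model (sections 5.0 and 5.3).
- **What follows in both arms.** Section 5.0: "After completion, patients will undergo standard of care procedures with the MMS team, including surgeon, and undergo the first stage of the MMS procedure". Under section 5.52, if a patient raises specific medical questions about the procedure, "the research assistant will defer to the medical team".
- **When satisfaction is measured.** Section 5.2, on the combined quiz and satisfaction form: "We propose to hand out this questionnaire following completion of the first stage of MMS". The table in section 5.4 agrees and lists no other satisfaction measure.
- **What is to be rated.** Section 5.2: "patients will be provided 3 subjective questions related to their satisfaction with the explanation of MMS that they received". In Appendix G, item 1 asks "Overall how satisfied are you with today's explanation of the Mohs Procedure" and item 2 asks "Do you feel that this explanation can be improved". Item 3 asks whether patients should be given an explanation of a similar kind. No item names a speaker, a place or a time of day.
- **What it is for.** Objective 3 in section 2.0 asks whether satisfaction is higher with the model and script than with standard of care.

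**The concern.** The item and the randomised component do not line up exactly. The arms differ in one session before surgery. The question covers the day, and by the time it is asked the patient has also met the surgeon and had the first stage. A patient could reasonably answer about the session, about what the team said, or about both together.

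Answers about information common to both arms add nothing to the between-arm contrast. If satisfaction came out equal, the reader could not tell whether the model makes no difference or whether some patients were rating something else. No other collected item separates the two, and the referent cannot be recovered afterwards.

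**Working it through.** **1. The plan's own figure.** Section 6.2 sizes the trial on STAI Form Y1: difference 6, SD 10, two-sided 0.05, power 80%.
- Normal approximation: n = 2(1.960 + 0.842)² × 10² / 6² = 43.6, so 44 per group.
- Two-sample t-test: 44.6, so 45 per group.
- With 10% attrition: 45 / 0.90 = 50 per group.

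The stated 45 and 50 reproduce. They concern STAI only, so the survey wording does not touch them. The plan gives no effect size, SD or power for satisfaction.

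**2. Does any text settle which explanation is meant?**
- Section 5.2 uses the singular but does not tie it to the research assistant's session.
- Section 5.51 says patients will be told about each instrument beforehand. It does not say they will be told which explanation to rate.
- Appendix G has no instruction above the items.

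The referent is therefore left open.

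**3. Is there a competing source of information before the survey?**
- Section 5.0 places contact with the surgeon and team between session and survey, in both arms.
- Section 5.52 sends certain questions to that team.
- Appendix A promises a fuller discussion of wound closure with the surgeon. This is weak support: closure is decided after the cancer is cleared, and the script says about half of patients need further stages, so that talk may come after the survey.

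Some information from the team before the survey is likely. A second full explanation is not documented.

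**4. Direction of the effect.** Let M_E and M_C be the mean ratings of the session in the two arms, M_T the mean rating of the team's information (taken as the same in both arms), and f the share of patients who rate the latter. Each arm's mean is (1 − f)M + f·M_T, so the observed difference is (1 − f)(M_E − M_C). This is dilution towards zero.

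It needs f and M_T to be equal across arms. With unequal shares the difference is (1 − f_E)(M_E − M_T) − (1 − f_C)(M_C − M_T), which can move either way.

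**5. Illustration only.** Both f and the effect size d are assumed. The value d = 0.6 is borrowed from the STAI calculation (6/10), and d = 0.5 is a second assumed value. Power is for a two-sided t-test at 0.05 with 45 per group, treating the rating as continuous with unchanged SD.

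| Share f | d = 0.6 becomes | Power | d = 0.5 becomes | Power |
|---|---|---|---|---|
| 0 | 0.60 | 80% | 0.50 | 65% |
| 10% | 0.54 | 72% | 0.45 | 56% |
| 25% | 0.45 | 56% | 0.375 | 42% |
| 50% | 0.30 | 29% | 0.25 | 22% |

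The table shows how sensitive the comparison would be. It does not estimate what will happen in this trial.

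**The case against.** The case against is substantial.

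- **No second explanation is documented.** Section 1.1 calls the comparator "the current standard of care, verbal counseling", which could be read as a separate talk by the surgeon. Section 5.0, however, presents the scripted session as the control arm's standard-of-care counselling, and its later reference to care with the team does not mention education. Deferral under section 5.52 applies only to certain questions, and only if a patient asks them. This stands, so the point cannot assert that the surgeon repeats the explanation.
- **Context helps the patient.** The satisfaction items follow a quiz that thanks patients for taking part in the study, and the research team supervises completion. This makes the session the likelier referent for many patients, but it does not fix it.
- **The effect can be overstated.** A reader might infer that the ratings carry no arm effect, or that item 3 cannot support the model at all. The documents do not bear that out. Objective 3 is worded around satisfaction during Mohs surgery and item 1 asks for an overall view, so a global rating still contains the randomised part. A difference on item 3 would be weakened, not made meaningless.
- **The size is unknown.** This also stands. A physical model is memorable, so the share could differ by arm and the simple dilution formula would then fail.
- **The team's information may not be identical across arms.** Section 6 allocates whole clinic days to one arm in advance, and no blinding of staff is described. This limits the claim of pure dilution, but it is another reason to point the item at the session.

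What survives is narrower: the wording leaves the referent open at a time when there is more than one candidate.

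**Conclusion.** The point holds as an inexpensive improvement to the only satisfaction measure. The survey should say which explanation it means. Without that, some ratings may reflect the team's information or a mixture. If that information and the share of patients rating it are similar in both arms, the Objective 3 difference shrinks towards zero and a null finding becomes ambiguous.

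No magnitude can be given from the documents, and the illustrative power figures should not be quoted as an expected loss. The STAI sample size is unaffected, and the trial was not sized on satisfaction.

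**What to change.** Before first use, reword all three Appendix G items so that they refer to the educational session before surgery. For item 1, for example: *How satisfied are you with the explanation of Mohs surgery you were given in the private room before your surgery today, just after the first questionnaires?* The last clause matters because the team may also see the patient before the first stage, whereas section 5.52 places the session directly after baseline testing. Items 2 and 3 should carry the same reference.

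Use identical wording in both arms and do not mention the model. Name the session rather than the research assistant, because the research team supervises completion and naming the person could invite courteous answers.

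**Cost.** Three lines of a survey written for this trial, with the usual minor notification to the ethics board. There is no extra burden or data, and the post-Stage-1 timing chosen for clinic workflow stays. The trade-off is that the items then measure satisfaction with the session, not with the whole day's explanation. Some courtesy bias may remain; it is expected to be similar in both arms.
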